18.0 Confidentiality

A. Confidentiality of Study Data

Describe the local procedures for maintenance of confidentiality of study data and any records that will be reviewed for data collection.

18.1 A. Where and how will all data and records be stored? Include information about: password protection, encryption, physical controls, authorization of access, and separation of identifiers and data, as applicable. Include physical (e.g. paper) **and electronic files.**

Response: All data will be immediately deidentified and stored on a secure, password protected server at the University of Buffalo. All deidentified measures will be stored in locked filing cabinets at each respective site. Data will be entered electronically into the Research Electronic Data Capture system (REDCap; project-redcap.org), a secure web application engineered for data collection purposes, or into data files on secure UB servers.

18.2 A. How long will the data be stored?

Response: The data will be kept on file for approximately 3 years following any professional publication according to the American Psychological Association guidelines. Deidentified, anonymous data will be kept in a database indefinitely.

18.3 A. Who will have access to the data?

Response: Only trained study personnel and staff will have access to the data.

18.4 A. Who is responsible for receipt or transmission of the data?

Response: Data that are collected from participants will be immediately stored electronically via REDCap, entered into data files on secure UB servers, or immediately placed into locked filing cabinets at the University at Buffalo. Only deidentified data will be available through the REDCap system. No other transmission or receipt of data will be necessary.

18.5 A. How will the data be transported?

Response: Not applicable. Recordings or study measures completed at either the University at Buffalo will stay at their respective site. Only deidentified data will be available through the REDCap system.

B. Confidentiality of Study Specimens

Describe the local procedures for maintenance of confidentiality of study specimens.

N/A: No specimens will be collected or analyzed in this research.
(Skip to Section 19.0)

18.6 B. Where and how will all specimens be stored? Include information about: physical controls, authorization of access, and labeling of specimens, as applicable.

Response:

18.7 B. How long will the specimens be stored?

Response:

18.8 B. Who will have access to the specimens?

Response:

18.9 B. Who is responsible for receipt or transmission of the specimens?

Response:

18.10 B. How will the specimens be transported?

Response:

19.0 Provisions to Monitor the Data to Ensure the Safety of Subjects

- N/A: This study is not enrolling subjects, or is limited to records review procedures only. This section does not apply.

NOTE: *Minimal risk studies may be required to monitor subject safety if the research procedures include procedures that present unique risks to subjects that require monitoring. Some examples include: exercising to exertion, or instruments that elicit suicidality or substance abuse behavior. In such cases, N/A is not an acceptable response.*

19.1 Describe the plan to periodically evaluate the data collected regarding both harms and benefits to determine whether subjects remain safe.

Response: *The principal investigator will oversee and be responsible for monitoring the safety and efficacy of the trial. An annual report will be sent to NIMH outlining recruitment of participants and their demographic characteristics and how these compare to expected recruitment rates, retention rates in the project, summaries of any adverse events, and any actions taken with respect to the protocol. The study will be approved by the University at Buffalo and Florida International University Institutional Review Boards.*

All data collected will be coded with study numbers (computer-generated data, videotapes, and paper ratings) and the sheet linking study code numbers to individuals will be keep in a locked filing cabinet inside a locked room. All data entered into computer databases will use study numbers to protect the confidentiality of the participants. Data entry will be checked by an individual other than whomever entered the data, and errors will be corrected and discrepancies corrected by a supervisor

based on the original source documents. Data will be entered and screened for accuracy immediately after it is obtained, and preliminary blind analyses will be conducted immediately after each funded year to determine whether the results indicate an overwhelming treatment effect that suggests the study should be stopped, or suggests any potential unforeseen adverse effect of the behavioral parent training programs. All source documents and recordings will be kept in locked filing cabinets inside a locked room.

Experimental integrity will be ensured by the creation of program manuals, checklists and materials to ensure consistent implementation of planned manipulation components. In addition, all sessions will be video-recorded so that the principal investigator can review implementation and provide feedback as necessary. Data will be collected by research assistants who have completed the Biomedical Sciences CITI course on research ethics, and who are trained by the study investigators in the research procedures.

The safety of all participants in these proposed studies is paramount. After the initial intake interview, records will be reviewed by the principal investigator to determine the participant's eligibility for the study. Careful attention will be directed toward any potential reports of child abuse or neglect or reports of suicidal ideation or behavior on the part of the parent or child. Should child abuse or neglect be suspected, the parent will be notified that a mandated report is being made to the state child abuse hotline. Any additional actions that might be necessary to ensure the child's immediate safety will occur. Similarly, if a parent reports suicidal ideation, intent, or behavior on the part of the child or parent, the participant will not be enrolled in the study, but instead directed to mental health or psychiatric treatment, and if interested can enroll in the project once their behavior has stabilized.

19.2 Describe what data are reviewed, including safety data, untoward events, and efficacy data.

Response: See response to 19.1

19.3 Describe any safety endpoints.

Response: Safety endpoints will be the collection of endpoint data in May

19.4 Describe how the safety information will be collected (e.g., with case report forms, at study visits, by telephone calls with participants).

Response: See response to 19.1

19.5 Describe the frequency of safety data collection.

Response: Data will be collected at intake, in January, and in May. Spontaneous reports will also be collected, documented and reviewed by the PI and the team at least weekly.

19.6 Describe who will review the safety data.

Response: Final review will be conducted by [name]

19.7 Describe the frequency or periodicity of review of cumulative safety data.

Response: At least weekly or more often if needed.

19.8 Describe the statistical tests for analyzing the safety data to determine whether harm is occurring.

Response: Each year, preliminary analyses will be conducted to ensure there is no untoward effect of the DRC intervention.

19.9 Describe any conditions that trigger an immediate suspension of the research.

Response: Documentation of a significant untoward effect of the DRC.

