DRC group. Students assigned to the DRC group will have a consultant assigned to the student for the duration of the school year. During the month of January, the consultant will work with the child's primary special education teacher (or regular education teacher if the child spends the majority of his or her day mainstreamed) to establish a DRC over the course of three consultation visits. The How to Establish a Daily Report Card manual contains a standard DRC instruction packet that is provided to teachers to explain the rationale of the DRC, procedures for creating, modifying, and evaluating the DRC, procedures for parents to create home-based rewards for DRC performance, and information on trouble-shooting. In addition, the packet contains consumable hand-outs that may be used to facilitate the meeting of these goals. This packet will be used as a starting point in all DRC consultations, and it was successfully modified, used, and evaluated in our Goal 2 project.

The first visit will be spent reviewing the IEP with the child's teacher(s) and conducting an interview to determine the behavioral procedures the teacher currently uses to manage child behavior as well as identify potential target behaviors not currently included on the IEP. At this meeting, target behaviors will be identified, operationally defined, and integrated into a DRC. The teacher will be asked to implement the intervention during the week between the first and second visit. At the second consultant visit, target behaviors will be refined, and using the data collected by the teacher, criteria for each target behavior will be modified (e.g., a child who averaged 10 verbally intrusive behaviors per class would have a target behavior changed to "Has 8 or fewer verbally intrusive behaviors"). The third consultant visit will be conducted to fine-tune and trouble-shoot the DRC and inform the teacher of the home rewards established by the parents. During this visit, the consultant will also establish a weekly time for the teacher to fax/call in a summary of DRC results for the week. DRCs will be implemented across settings and classes; however, a single teacher will be identified for assessment completion, observations will be conducted in that teacher's class, and this individual will be required to attend all consultant meetings.

The DRC will include direct accounting for IEP goals as well as other behavior problems common to a child with ADHD, and it is necessarily

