idiosyncratic to address the heterogeneity that is typical in samples of children with ADHD. For example, a child with an IEP due to low achievement in reading, who also exhibits disruptive behaviors and noncompliance, might have targets established such as “Completes assigned reading tasks with 80% or better accuracy;” “Interrupts class discussion 4 or fewer times per class/interval;” and “Has 2 or fewer instances of noncompliance during the transition to lunch.” A standard list of common DRC goals has been created and will be used to facilitate initial target behavior selection. These goals clearly overlap with the actual goals created as part of the development project ([name] et al., 2010). The DRC would be evaluated and completed by the teacher daily, and feedback will be provided to the child throughout the day on progress made toward DRC goals.

At the end of each day, the teacher will send the DRC home with the child so that the parent is provided feedback on a daily basis regarding the child’s behavior at school. Parents will attend three individual parent training meetings to introduce them to the DRC also conducted in January in the child’s school, and they will establish home-based rewards contingent on the child’s DRC performance. For example, for a child with three DRC goals evaluated twice per day (i.e., before lunch and before dismissal), there are six possible “yes’s.” A given parent might remove computer access for this child previously provided non-contingently and only provide 10 minutes for each “yes” reported for the day (i.e., a child who earned all “yes’s” on a particular day would be rewarded with 60 minutes of computer time). This binary approach of yes/no is easier to explain to the child, and permits the child to track his/her own progress across the day (i.e., number of yes’s earned), relative to a continuous rating, which may be harder for the child to comprehend/quantify. In addition to the home-based contingency management based on school feedback, which makes the child accountable at home for school-based behavior, the DRC serves as a mechanism of daily communication between the parent and teacher. Given the variability in behavior expected with a child with ADHD, such daily communication is often crucial for preventing deterioration in functioning and presents the parent and teacher with multiple opportunities to problem-solve.

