After the three initial meetings with the child’s teacher, consultants will meet monthly with the teacher (and parent if available) to provide feedback on the child’s behavior during the month using a graphical representation of the child’s DRC performance. This information will be used for data-driven decision making, a procedure shown to be better than teacher impressions/judgments when intervention planning/monitoring (Fuchs et al., 2000) and potentially critical for IEP monitoring. DRC goals will be adjusted as needed. It is expected that these monthly meetings will serve the purpose of ensuring IEP goals and objectives are consistently addressed on the DRC throughout the year.

SAU group. Consultants will conduct an initial meeting with each teacher of children in the SAU group to describe study procedures, establish regular classroom observation times, and obtain an updated copy of the child's IEP. All procedures will be implemented in the IEP as planned (e.g., counseling, school interventions). This condition is conceptualized as a school as usual control and serves as the counter-factual condition for the study.

To account for consultant contact with the teacher, consultants will meet with the teachers in the SAU group once per month. During these meetings they will collect information on how the child is functioning, and obtain information on any new, discontinued, or modified interventions (reward and/or punishment). The consultant will work with the teacher to construct a list of goals and criteria for meeting goals consistent with the approach used in the DRC group. This list of goals will not be used to develop DRCs or other classroom interventions but will be used by the observer to record teacher feedback to the child related to targeted behaviors. Our goal 2 study had teachers fill out an Individualized Target Behavior Checklist (ITBC; [name], [name], & Massetti, 2005), which was constructed in the same manner as a DRC, but feedback on target behaviors was not provided to the child or parents and contingencies were not provided at school or home. Our Goal 2 study suggested that the ITBC had no appreciable effect on behavior ([name] et al., 2009, 2010) replicated by other studies ([name], [name], et al., 2016).

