Fidelity of Teacher Implemented Interventions. Observers will collect information each month (January to May) on teacher responses to student behavior and general classroom management techniques. These observations will include a recording of frequency counts of social reinforcement (e.g., praise statements) as well as commands and negative feedback (i.e., reprimands) directed toward the individual student across the entire school day. These frequency counts will be combined into a ratio of positive to negative statements and used as an indicator of classroom environment. After each observation, observers will also complete a post-observation inventory form. These forms will ask the observer to rate the teacher's use of social reinforcement, commands, tone of voice, and the overall classroom climate on a 7-point Likert scale. An example of this rating to be completed after the observation is in Appendix C.

Integrity of DRC/Targeted Behavior Feedback. Once per month, observers blind to treatment group assignment will spend a full school day in the child's classroom. The observer will be provided a copy of the child's DRC/ITBC and will record a frequency count of the occurrence of each targeted behavior. In addition, targeted behaviors for which the child received specific feedback from the teacher (i.e., were acknowledged; recorded on the DRC/tracking mechanism if appropriate) will also be recorded. This will yield a daily rate of target behavior occurrence, as well as the proportion of targeted behaviors that received appropriate feedback. Observers will also record the latency between the occurrence of a targeted behavior and teacher feedback regarding the behavior using a stop-watch (a decision rule of latency greater than 1 minute will be used to document "no response" to a target behavior).

For children in the DRC group, we will be able to obtain a sample of the proportion of DRC targets appropriately monitored by the teacher with feedback provided. The observer's completed DRC tracking sheet will also be compared to the DRC completed by the teacher to ascertain a sample of the accuracy of the report sent home to the parent each afternoon. This comparison will be made by the investigators/project coordinator to maintain observer blinds.

Integrity of Home Rewards for School Performance. Following each of the all-day school observations (i.e., monthly), SAU/DRC families will be

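### Between January and May the only named harm route is spontaneous reports, scheduled study contact is unequal between arms, and section 19.8 does not say which data the yearly harm check uses

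*Combined protocol and SAP*

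**What the plan says.** **Safety collection.** Section 19.5 gives the schedule: "Data will be collected at intake, in January, and in May". It then adds: "Spontaneous reports will also be collected, documented and reviewed by the PI and the team at least weekly". Section 19.3 states: "Safety endpoints will be the collection of endpoint data in May". Section 19.4, on how safety information is gathered, only points back to 19.1, and 19.1 contains no adverse-event definition, form or question.

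**Yearly check.** Section 19.8 reads: "Each year, preliminary analyses will be conducted to ensure there is no untoward effect of the DRC intervention". It names no data source, test or threshold. Section 19.1 calls the yearly preliminary analyses blind and promises an annual report that summarises adverse events. Section 19.9 makes a documented significant untoward effect of the DRC the condition for immediate suspension, and does not define significant.

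**Scheduled contact.** In the DRC arm (10.1) there are three teacher visits in January, and at the third "the consultant will also establish a weekly time for the teacher to fax/call in a summary of DRC results for the week". For families, "Parents will attend three individual parent training meetings to introduce them to the DRC", also in January. Monthly meetings with the teacher follow, joined by the parent if available. In the SAU arm there is one initial teacher meeting, and then: "To account for consultant contact with the teacher, consultants will meet with the teachers in the SAU group once per month". Both arms share a family contact (10.2, Integrity of Home Rewards for School Performance): "Following each of the all-day school observations (i.e., monthly), SAU/DRC families will be" called or texted the next morning and asked about home consequences for school behavior.

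**The concern.** A spontaneous report needs someone to volunteer it, and meetings and calls with study staff are occasions to do so. When one arm has more of these occasions, a difference in report counts mixes true harm with opportunity to report. The protocol accepts this principle for efficacy: the SAU monthly meeting exists to balance consultant contact. That balancing does not extend to the parent meetings, the extra January visits or the weekly teacher report.

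What is at stake is the trial's statement on the safety of the DRC. The yearly check in 19.8 leads to the suspension condition in 19.9, and the annual report is a second place where adverse events could be set out by arm. Because 19.8 does not name its data, there are two possibilities, and each leaves a gap. Report counts are exposed to unequal ascertainment. May data are collected on the same schedule in both arms, but the measures described in 10.2 include none that asks about harms during treatment.

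**Working it through.** The documents state no contact ratio, adverse-event rate, safety test or safety power, so there is no planned figure to reproduce. The check is a count of scheduled contacts per child, followed by a reading of what each possible data source would capture.

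**Inputs (sections 10.1 and 10.2)**
- January teacher visits: DRC 3, SAU 1. Difference 3 − 1 = 2.
- January parent meetings: DRC 3, SAU none described.
- Monthly teacher meetings: both arms, about 4 each (assumed February to May).
- Next-morning family call or text: both arms, about 5 each (one per monthly full-day observation, January to May).
- Weekly teacher fax or call: DRC only. Treatment lasts 16 to 20 weeks, so up to 20. About 13 if it starts only after set-up (assumption).
- Observer visits: both arms, 5 full-day plus 6 for the primary outcome = 11.

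**Ratio of DRC to SAU contacts under different counting rules**
- February to April, meetings and family calls only: (3 + 3)/(3 + 3) = 1.0. Adding 12 weekly reports: 18/6 = 3.0.
- Whole period, meetings and family calls: (3 + 3 + 4 + 5)/(1 + 4 + 5) = 15/10 = 1.5. Adding 20 weekly reports: 35/10 = 3.5.
- The same with observer visits: (15 + 11)/(10 + 11) = 26/21 = 1.2. Adding 20 weekly reports: 46/21 = 2.2.
- Family contacts only: (3 + 5)/5 = 1.6, or (3 + 4 + 5)/5 = 2.4 if the parent joins every monthly DRC meeting.
- Consultant contacts only: (3 + 3 + 4)/(1 + 4) = 10/5 = 2.0. Adding 20 weekly reports: 30/5 = 6.0.

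The ratio therefore runs from about 1.0 to 6.0. None of these rules puts it below 1, but no single value can be defended as the exposure to reporting. The higher values come from the weekly fax or call. The other extra contacts sit in January, apart from any parent attendance at the monthly DRC meetings.

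**What each source would capture**
- *Spontaneous reports:* they cover the treatment weeks, but with unequal opportunity to report.
- *May data (19.3):* collected alike in both arms. They can show a child who is worse in May. They are not described as asking about events that arose and resolved earlier. Section 21.1 describes the foreseeable discomforts of the measures and the intervention as mild and transitory, which is the kind of event a May assessment can miss.
- *Matched monthly contacts:* they cover the treatment weeks equally, but their described content is not a harm inquiry. The family call asks about home consequences, the DRC meeting reviews a graph of DRC performance, and the SAU meeting asks how the child is functioning and which interventions have changed.

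**The case against.** The strongest reply is that the documents never say the yearly check uses spontaneous reports. Section 19.3 names the May data as the safety endpoint, 19.1 describes the yearly analyses as blind, and 19.5 links spontaneous reports only to weekly review by the investigator's team. If the check uses May data, contact frequency does not bias it in this way. That reply stands, and it makes the bias conditional. It does not supply the missing data source in 19.8. It also leaves the treatment weeks without a described solicited measure. Blinding the analyst would not equalise the opportunity to report.

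Second, contact is better matched than it first appears. The extra teacher visits and parent meetings fall in January, while monthly teacher meetings and family calls run in both arms. The weekly item is a summary of DRC scores that may be faxed, not a conversation about harm. SAU teachers are asked how the child is functioning, so that arm has some active inquiry. All of this stands and limits the likely size.

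Third, the table of measures (10.3) and the consultant checklists (17.3) were submitted separately and are not visible here. A harm question could be in them, so the claim is limited to the visible text.

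A reader might go further and infer a specific contact ratio, a probability that the yearly check falsely shows harm, or a likely wrongful suspension. The documents support none of these. The ratio depends on the counting rule. A false-signal probability would need a report rate per contact, strict proportionality of reports to contacts, and a test, none of which is stated. Section 19.9 asks for documentation of a significant effect and sets no numerical or automatic rule, so an imbalance in counts would not by itself suspend the trial.

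**Conclusion.** The point holds in conditional form. In the visible text, harms between the January and May collections are unsolicited, scheduled contact favours the DRC arm, and 19.8 does not name the data for its yearly check. If spontaneous reports enter that check or an arm-level adverse-event summary, the comparison is open to ascertainment bias, most plausibly toward more recorded DRC events. If only May data are used, no solicited harm measure covers the treatment weeks.

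This rests on one assumption from outside the documents: that volunteering a report depends at least partly on having occasion to speak with study staff. The size of any bias cannot be derived, and no false-alarm rate should be attached to it. Severity is minor to moderate: the risks listed in 21.1 are mostly mild and contact is largely matched after January, but the comparison bears on the trial's safety statement. It is best treated as a cheap improvement to the method of collecting harms.

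**What to change.** - **19.4 and 19.5:** add one adverse-event question, worded identically in both arms, to the monthly family call or text and to the monthly teacher meeting. Both arms already have these contacts, so no new visit is needed. If the separately submitted measures or checklists already contain such a question, cite it here and confirm that both arms receive it in the same words.
- **19.8:** state that the comparison of arms uses these solicited events together with the January and May data, and that spontaneous reports serve only the weekly case review. Apply the same rule to any adverse-event summary given by arm in the annual report.

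The cost is a wording change, slightly longer calls and meetings, and more minor events to record. In return, harms during the treatment weeks are asked about equally in both arms.
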